5. SAMPLE SIZE CONSIDERATIONS

Surviving patients from Study IMM-101-001 (EudraCT number: 2009-012447-42) who were continuing to receive IMM-101 on a Named Patient Programme (NPP) basis were invited to enrol into study IMM-101-008.

6. ANALYSIS POPULATIONS

The Safety Population will comprise all patients who receive at least one dose of the study drug in the LTF study. All members of the Safety Population had previously been enrolled into the FIH study. Analysis of safety and tolerability endpoints and efficacy endpoints will be summarised on the Safety Population.

7. GENERAL CONSIDERATIONS FOR DATA ANALYSES

In general, continuous data will be summarised using mean, standard deviation, minimum, median and maximum. The minimum and maximum will be recorded to the same number of significant figures as the

original data, whilst mean and median will be presented to 1 significant figure more than the original data, and standard deviation 2 significant figures more than the original data.

In summaries of categorical data, frequency counts and percentages will be used. Generally, percent will be displayed to one decimal place.

The time to event variable OS will be analysed using standard Kaplan-Meier techniques. The Kaplan Meier curve will be plotted and median (50%), 25% and 75% survival estimates reported with the corresponding 95% confidence intervals (CIs).

All analyses will be performed using SAS v 9.4 (or higher).

All tables, figures and listings (TFLs) will include titles, headers or footnotes which identify:-

- The analysis set on which the presentation is based.
- A description or title for the presentation (where combined data is presented from the FIH study and the LTF study, this will be indicated).
- The date and time the output was produced.
- A reference to the name and location of the file used to produce the output and the source of the data used (which may be a SAS dataset or another TFL).
- Reference to the analysis stage of the study data e.g. Final Analysis.

Listings which present data using repeating rows for a patient and/or visit will be presented in chronological date order (where applicable) with the repeating header information presented on the first new record for each repeating combination only, to facilitate readability.

All assessment data will be reported with the visit at which it was recorded, whether or not the visit falls inside the relevant window or not.

Tables and figures will be coded from Analysis Data Model (ADaM) format datasets. Listings will be coded from Study Data Tabulation Model (SDTM) datasets.

8. DATA HANDLING CONVENTIONS

8.1 Premature Withdrawal and Missing Data

Patients who withdraw early will be included in the analysis of safety and efficacy. Missing, unused and spurious data will be treated as such. No imputation methods will be applied, except for concomitant medication stop date as follows:

If the stop date for a medication is partially missing, it will be assumed to be a concomitant medication if, based on the partial information available, concomitant is not ruled out. Hence the date will be imputed to the end of the month/year, i.e. if day is unknown it will be set to the last day of the specified month, if day

and month are unknown it will be imputed as 31st December. This imputation will be also used in the determination of whether the previous medication was stopped within 14 days prior to Day 0.

Date imputations will not be shown in data listings however, the flag based on imputed dates will be shown in the listings. Date imputations will be incorporated into tabulations of previous/concomitant medications.

8.2 Prior and Concomitant Therapy and Medical History Melanoma Therapies Coding

Each concomitant therapy recorded during the FIH and LTF studies will be categorised according to anti-melanoma cancer therapy type as follows:

- Chemotherapy
- Cancer surgery (note: melanoma cancer surgeries only are included in this category)
- Radiotherapy
- Immunotherapy (other than IMM-101)
- Radiofrequency ablation
- Immunotherapy IMM-101.

Other categories may be considered, if relevant and mutually exclusive to the above.

A look-up table will be created containing the relevant verbatim term, dataset location and therapy code. Exploristics will supply dataset(s) in Excel format where verbatim terms for therapies contained in the previous and concomitant medications, and medical history datasets are listed, for allocation to one of the anti-melanoma cancer therapies codes by Immodulon. These will be medically reviewed by Immodulon and approved prior to issue of final TFLs. Listings will include the assigned categories, where allocated.

All concomitant therapy groupings with the exception of immunotherapy IMM-101 will be included in the tabulation of anti-cancer (melanoma-related) therapies. Therapies included will be all therapies given after first dose of IMM-101 in the FIH study, including co-medication during NPP treatment (recorded as medical history since leaving the FIH study) and during the LTF study.

8.3 Derived and Transformed Data

As age was not collected it will be derived using the patient's date of birth and date of consent. The derivation will be

Age (years) = integer part of ((patient informed consent date - date of birth + 1)/365.25).

Note that the full date of birth will be used in the calculation, but only year of birth will be listed. Patient initials will not be listed.

Time since initial diagnosis of current presentation, time since excision of primary lesion, time since excision of sentinel node and time since regional lymph node resection will be derived in years as follows;

Time since initial diagnosis of current presentation (years) = (Day 0 - date of initial diagnosis of current presentation + 1) / 365.25

Time since excision of primary lesion (years) = (Day 0 - date of excision of primary lesion + 1) / 365.25.

Time since excision of sentinel node (years) = (Day 0 - date of excision of sentinel node + 1) / 365.25 and missing if not excised.

Time since regional lymph node resection (years) = (Day 0 - date of regional lymph node resection + 1) / 365.25 and missing if not resected.

The relevant time variable above will be reported to 1 decimal place, but calculated using all accuracy available in the data. If any dates are partial, i.e. day number missing, the time variable will be calculated using month and year only and if day and month missing, the time variable will be calculated using year only as follows:

- If only month and year are present (MMYYYY): Time since Event = (Day 0 – Event date +1) / 365.25;
- If only year is present (YYYY): Time since Event = (Day 0 – Event date) +1 / 365.25.

The total number of pre-study doses of IMM-101 received (since the completion of study IMM-101-001) will be calculated for each patient.

Exposure during the IMM-101-008 study will be summarised by time on study in years and overall exposure in months, which will be derived using:

Time on study (years) = (date of study completion (i.e. death on study)/date of withdrawal) - Day 0 + 1) / 365.25.

Overall study drug exposure (months) = (date of last dose - date of first dose in study IMM-101-008 + 1) / 30.4375.

Overall exposure of IMM-101 (FIH and LTF study combined) will be derived using:
(date of last dose in study IMM-101-008 – date of first dose in study IMM-101-001 + 1) / 30.4375.

On-study dosing will be summarised using the total number of doses on study:

Total no. doses on study = (Total number of IMM-101 doses whilst on the LTF study by totalling the doses (full or part doses counted as 1 dose) recorded in the CRF.

Time elapsed since previous dose (for on-study administration of IMM-101) will be derived using;

Time elapsed since previous dose (days) = (date of current dose - date of previous dose + 1).

A **dose change flag** (Dose changed from previous dose, I = increased, D = decreased) will be used to record any escalation or reduction in dose received between consecutive visits. If the dose has remained consistent compared to previous dose, this flag will remain unoccupied.

Time to event analysis will be performed on OS which will be calculated in years, from Day 0 in study IMM-101-008 using;

Overall Survival (years) = (date of death - Day 0 + 1)/365.25
OR (censored date - Day 0 + 1)/365.25

See Section 10 for additional information.

Adverse events and medical history will be coded using MedDRA v 18.0 (or higher). MedDRA will be used to create System Organ Class (SOC) and Preferred Term (PT) variables.

A **flag (Stopped >14 days prior)** will be created for previous medications which were taken and stopped before 14 days prior to the end of screening procedures (i.e. Day 0) based on the medication end date and date of Day 0.

Previous and concomitant medications and significant medical history since completing the FIH study will undergo coding for anti-melanoma cancer treatments, see Section 8.2.

Note: Derived variables recorded in the unit of months or years will be reported to 1 decimal place, derived variables recorded in the unit of days will be reported to whole numbers only. Age will be reported to whole years only.

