Note: As patients may have more than one lesion in various locations they can be included in more than one location category.

Note: Percent is based on the number of patients who provided a response for each criteria.

Note: Time (years) since variables are calculated from Day 0 + 1 and divided by 365.25.

Code: S:\Services\Immodulon\IMM-101-008\Analysis\Development\Code\Table3a.sas ddmmmyy:hh:mm:ss

Data: S:\Services\Immodulon\IMM-101-008\xxxxx.sas7bdat

Note to programmer: Please update data footnote with appropriate file directory.

Note to programmer: Locations listed under PELOC e.g. Lung.

Note to programmer: If stage is other and more information is provided include it in the other description or as a footnote.

Note to programmer: Decimal places for continuous data summaries are based on the variable recorded in the data being to zero decimal places. If the decimal places recorded are increased in the data then increase decimal places for mean, median, SD, min and max in the table accordingly.

Note to programmer: Please add footnote if any 'time since' variables contain partial missing dates, see SAP section 8.2: Where day and month are not known for either date, calculation is based on year alone: Time since event (years) = (Year of Day 0 - Year of event) + 1/365.25, likewise if day is not known for either date, calculation is based on month and year only

CONFIDENTIAL**Exploristics Limited**

Identifier: EXP12002

Clinical Study Identifier: IMM-101-008

Final Analysis

Protocol: IMM-101-008

Analysis Population: Safety Population

Page x of y

Table 3b

Significant Medical History since Completion of Study IMM-101-001

System Organ Class Preferred Term	N = xx (%)
Significant or clinically relevant medical history since completion of study IMM-101-001?	N
Yes	xx (xx.x)
No	xx (xx.x)
Unknown	xx (xx.x)
If Yes:	
System Organ Class Preferred Term 1	N
Preferred Term 2	xx (xx.x)
Preferred Term n	xx (xx.x)

Note: Medical History is coded using MedDRA version xx.x.

Note: Percent is based on the number of patients in the Safety Population.

Code: S:\Services\Immodulon\IMM-101-008\Analysis\Development\Code\Table3b.sas ddmmmyy:hh:mm:ss

Data: S:\Services\Immodulon\IMM-101-008\xxxxx.sas7bdat

Note to programmer: Please update data footnote with appropriate file directory.**Note to programmer:** Please add relevant MedDRA version number in note to reflect version used at time of coding.**Note to programmer:** Sort SOC and PT by decreasing incidence.

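### The SAP's year-only rule for 'time since' variables discards the known month and day of Day 0 and can be wrong by almost a year; the month-year rule is ambiguous

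*SAP*

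**What the plan says.** SAP 8.3 uses one formula for time since diagnosis, primary excision, sentinel node excision and regional node resection when dates are complete, for example "Time since excision of primary lesion (years) = (Day 0 - date of excision of primary lesion + 1) / 365.25". On precision it says: "The relevant time variable above will be reported to 1 decimal place, but calculated using all accuracy available in the data".

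For partial dates it says that, when the day is missing, "the time variable will be calculated using month and year only", and that the year alone is used when the month is missing too. It then has two lines:

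- Month and year known: "If only month and year are present (MMYYYY): Time since Event = (Day 0 – Event date +1) / 365.25".
- Year known: "If only year is present (YYYY): Time since Event = (Day 0 – Event date) +1 / 365.25".

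The note to programmers under Table 3a (SAP 13.2) gives the year-only rule in calendar years, "Time since event (years) = (Year of Day 0 - Year of event) + 1/365.25", and adds "likewise if day is not known for either date, calculation is based on month and year only". The note under Listing 4aii repeats the year-only rule without the month-year clause. Both notes refer to SAP section 8.2, but the rule is in 8.3. SAP 8.1 allows no imputation except for the stop date of a concomitant medication.

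**The concern.** Day 0 is a study visit date and is known in full; only the event date is partial. Taking the difference of two calendar years throws away the month and day of Day 0 and returns a whole number plus 0.003. Two patients with the same year-only event, one treated first on 31 December and the other on 1 January, would get values a full year apart for a true difference of one day.

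The month-year line prints the full-date expression but tells the programmer to work from month and year alone. It does not say in what unit the difference is taken or which day is assumed, and assuming a day would go against 8.1.

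At stake is the description of disease duration in a small cohort.

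**Working it through.** The SAP gives formulas but no worked value, so there is no figure to reproduce. The check applies each rule to complete dates and compares the result with the SAP's own full-date formula, T = (Day 0 − event date + 1)/365.25. The dates below are assumptions, because the documents give no patient's dates.

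**1. Year-only rule, extremes.** R = (year of Day 0 − year of event) + 1/365.25.

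- Event 31 Dec 2008, Day 0 1 Jan 2012: T = (1,096 + 1)/365.25 = 3.003; R = 4 + 0.003 = 4.003; error +1.00 year.
- Event 1 Jan 2008, Day 0 31 Dec 2011: T = (1,460 + 1)/365.25 = 4.000; R = 3 + 0.003 = 3.003; error −1.00 year.

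Over all 865,524 pairs with Day 0 from 15 Sep 2011 to 31 Dec 2012 and the event from 1 Jan 2005 to 31 Dec 2009, the error runs from −0.999 to +0.999 year.

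**2. Year-only rule, average error by position of Day 0** (event equally likely on any day of 2008).

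| Assumed Day 0 | R | T, range | Error, range | Mean error |
|---|---|---|---|---|
| 1 Dec 2011 | 3.003 | 2.92 to 3.92 | −0.92 to +0.08 | −0.42 |
| 15 Jan 2012 | 4.003 | 3.04 to 4.04 | −0.04 to +0.96 | +0.46 |
| 1 Jul 2012 | 4.003 | 3.50 to 4.50 | −0.50 to +0.50 | about 0 |

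The bias therefore depends on where in the calendar year the patient started.

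**3. Year-only date with full Day 0 and the event set to 1 July.** Over the same pairs the error runs from −0.498 to +0.501 year, with mean 0.003. The maximum falls from about 1.0 to about 0.5 year. The rest cannot be removed, because the event's month is unknown.

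**4. Month-year rule on a day scale.**

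- Both dates set to the 1st of the month: error −0.082 to +0.082 year.
- Full Day 0, event on the 1st: 0 to +0.082 year.
- Full Day 0, event on the 15th: −0.04 to +0.04 year.

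Example: event 20 May 2009, Day 0 15 Nov 2011. T = (909 + 1)/365.25 = 2.491. With the event set to 15 May the result is (914 + 1)/365.25 = 2.505.

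**5. Effect on a summary.** The number of patients is assumed to be 10 to 12. The protocol (4.2) has 18 eligible patients, of whom 3 + 1 + 2 = 6 had stopped by August 2011, leaving 12; the SAP's panel plots are laid out 2 × 5 = 10. One year-only date with an error of 0.997 year (the second example in step 1, unrounded) moves a mean by 0.997/12 = 0.08 to 0.997/10 = 0.10 year.

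**The case against.** The best defence is that little depends on this. The rules apply only if dates are partial, and nothing in the documents shows that any are. The results are baseline descriptors, no inference is planned, Table 3a also gives medians, Listing 4ai shows the recorded dates, and a footnote is already required where partial dates are used. About half of the maximum year-only error would remain under any rule, and for a Day 0 in mid-year the SAP's rule is no worse on average than a 1 July rule. All of this stands, and it sets the size of the point. It does not justify discarding a date that is known.

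A reader might go further and infer that the SAP divides a count of months by 365.25. A 30-month interval would then come out as (30 + 1)/365.25 = 0.085 year against a true 2.491. The documents do not support this. The month-year line is the same expression as the full-date formulas, its added 1 and its divisor belong to a day scale, and nowhere is the difference called a count of months. Where the unit is years, the shell note says so and leaves the difference undivided. What can be said is that the wording does not rule that reading out.

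A reader might also take the bracket in the year-only line of 8.3 for a mistake. For a difference in calendar years, dividing only the one-day term is dimensionally right, and the shell notes confirm that meaning. The line would misfire only if programmed with day-valued dates: 1 Jan 2009 to 15 Nov 2011 would then return about 1,048, which is days.

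**Conclusion.** The year-only rule is a stated rule that gives poorer values than the data allow, against the SAP's own precision statement. Its error can reach almost 1 year either way, twice what is unavoidable, and its average depends on when in the year Day 0 falls. That result rests on the calendar-year reading, which the shell notes make explicit; the worked dates are illustrative.

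The month-year rule is ambiguous rather than shown to be wrong: on its natural day-scale reading it is good to about 0.08 year, but it needs an assumed day that the SAP neither states nor permits.

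The consequence is minor and confined to Table 3a and Listing 4aii. Overall survival has its own formula, from Day 0 to death or censoring, and is not affected.

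**What to change.** In SAP 8.3, replace the two partial-date lines with one rule:

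- Always use the full Day 0 date.
- Set a missing day to the 15th, and a missing day and month to 1 July.
- Cap the imputed date at Day 0 so that no interval is negative, and keep it consistent with the patient's other known dates.
- Apply (Day 0 − event date + 1)/365.25 throughout.

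Add these dates as an exception to the no-imputation statement in 8.1. Replace the programmer notes under Table 3a and Listing 4aii with the same rule, and correct their cross-reference from 8.2 to 8.3. Keep the planned footnote for affected values.

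The cost is a few lines in 8.1, 8.3 and two shells, plus a small programming change. No new data are needed.

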#### **3.3 CLINICAL FINDINGS**

**Study Number IMM-101-001:** This was an open-label, dose-escalation, intra-patient, placebo-controlled study, in adult patients with confirmed diagnosis of stage III or IV melanoma to evaluate the safety and tolerability of three doses of IMM-101.

A total of 19 patients were enrolled into the study between 10 March 2010 and 27 July 2010, and the study was completed by 23 September 2010; six patients received placebo followed by 3 doses of IMM-101 0.1 mg, six patients received placebo followed by 3 doses of

---

CONFIDENTIAL

Immudalon Therapeutics Ltd.  
[name]

IMM-101 0.5 mg, and six patients received placebo followed by 3 doses of IMM-101 1.0 mg, over a 4 week period. One patient received placebo followed by 2 doses of IMM-101 0.5 mg but was withdrawn after the second dose of IMM-101 as they were found retrospectively to have been ineligible at study entry due to brain metastases; an additional patient was recruited to this dose cohort to ensure data on six patients were collected.

The placebo injection was administered on Day -3 and the IMM-101 injections over a 4-week period (Day 0, 14 and 28). All injections were administered intradermally. At each dosing level, one patient was administered IMM-101 at least 24 hours in advance of the remaining patients in order to review safety evaluations and observe local injection site reactions. The decision to dose-escalate was preceded by a comprehensive review of safety data from the previous dose cohort.

There were no dose limiting toxicities observed and no evidence to suggest a clinically significant impact upon haematological indices, biochemical parameters or cardiac function. All documented changes in vital signs from screening to end of study were unremarkable.

There were no treatment-emergent adverse events (AEs) reported in the period following the placebo injection and before the first dose of IMM-101 – thus allowing a clear definition of the tolerability of the test product.

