### **2. Treatment**

Patients can receive ongoing treatment every 4 weeks or as close to this interval as permitted due to practical or logistic considerations until death or withdrawal, unless such therapy is contraindicated, the patient does not wish to continue or the study is terminated by the Sponsor. At no point should the elapsed period between IMM-101 doses be less than 14 days. The Study Flow Chart of Assessments is provided as Appendix 1.

Patients may choose to withdraw from the study at any time and for any reason. IMM-101 should be stopped or the dosing regimen reduced if felt to be necessary by the Investigator and/or patient (e.g., intolerable injection site reactions). In the event of an injection site reaction of Grade 3 and above, and/or if significant ulceration, tenderness or lymphadenopathy is observed, at the discretion of the Investigator, patients may be administered a half dose of the study drug (i.e., a single 0.05 mL intradermal injection of IMM-101) or the timing of the injection may be delayed. If the dosing interval is increased, the patient should still attend the study site for safety assessments preferably every 3 months but, if this is not possible, every 6 months at a minimum. In addition, if the patient does not attend the clinic for a study visit within a calendar month, the clinic will telephone the patient to enquire about injection site reactions, adverse events, concomitant medications and any other concerns. Details of the call will be recorded in the patient notes with appropriate information on adverse events and concomitant medications also being recorded in the CRF. The blood sample for exploratory analysis should continue to be taken every 6 months.

Any change in the dose of study drug administered or the frequency of dose administration should be recorded in the patient's case report form (CRF). In the case of withdrawal, separate consent will be sought to allow the continued collection on patient status.

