#### **Subsequent Visits at nominal 4 week intervals**

- Check that at least 14-days have elapsed since the last dose of IMM-101.

---

CONFIDENTIAL

Immudulon Therapeutics Ltd.  
[name]

- Assess injection site reactions.
- Any concomitant medications.
- AE/SAE reporting.
- IMM-101 administration (intradermal injection).

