## **7.3            *SELECTION OF DOSES IN THE STUDY***

A dosing schedule with IMM-101 which includes a period of induction, characterised by a series of administrations at close intervals followed by a maintenance phase with a single administration on a monthly basis has been proposed. It is believed that the period of induction will act by priming and boosting the patient's own immune system which, following a resting period during which anti-tumour immune responses can become established, would then require only periodic administrations or occasional boosting to maintain them.

The concept of priming and boosting has been used in other immunotherapeutic approaches to cancer with effective results. In a series of clinical investigations, Prostvac™, a prostate cancer immunotherapeutic regimen consisting of viral vectors containing transgenes for prostate-specific antigen and T cell co-stimulatory molecules, was administered in a primer step followed by multiple administrations as boosters [3, 4].

It is proposed that IMM-101 priming and boosting steps may stimulate both innate and adaptive immunity. It may act by rapidly activating cells of the innate immune system, including natural killer (NK) cells and macrophages, and through repeated stimulation it may elicit adaptive immune responses aimed at boosting anti-tumour responses. Compared to the immediacy of innate immune responses, adaptive immunity requires time to develop and may benefit from repeated stimulation to boost cellular involvement thereby eliciting more effective immune responses. Once fully established, adaptive immunity will only require regular administrations to maintain the responses.

The Phase I safety study was an intra-patient placebo-controlled study, to evaluate the safety and tolerability of 3 doses namely 0.1 mg (1 mg/ml), 0.5 mg (5 mg/ml), and 1.0 mg (10 mg/ml) of IMM-101. The dosing schedule was 3 doses of IMM-101 given at two-week intervals i.e. a period of induction or priming. In the intervening period between completing the Phase 1 study and enrolling onto this long term follow up study most patients will have been receiving IMM-101 at approximately four-week intervals, i.e., on a 'maintenance' cycle of one dose per month. It is proposed that this monthly maintenance cycle be continued in this long term study.

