11. PROTOCOL DEVIATIONS AND DEVIATIONS FROM PLANNED ANALYSIS

Protocol deviations will be reported separately, based on the study protocol deviations log maintained by Immodulon, and included in the CSR directly.

Any substantive deviations from the planned data presentations and analysis described in this SAP will be documented along with reason for change, in the CSR.

Overall survival will be calculated from the date of Day 0, not enrolment into the study, as the enrolment period may be up to 28 days long.

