Listing 9
Previous IMM-101 Administrations Since Completion of Study IMM-101-001

Unique Patient ID	Date of Last Administration of IMM-101 in Study IMM-101-001 (DD-MM-YYYY)	Administration Date of IMM-101 Since Completion of IMM-101-001 (DD-MM-YYYY)	Dose (mg)	Injection Site (R or L Deltoid)
xxxxxx	DD-MM-YYYY	DD-MM-YYYY	x.xx	xxxxxx
xxxxxx	DD-MM-YYYY	DD-MM-YYYY	x.xx	xxxxxx
xxxxxx	DD-MM-YYYY	DD-MM-YYYY	x.xx	xxxxxx
xxxxxx	DD-MM-YYYY	DD-MM-YYYY	x.xx	xxxxxx
xxxxxx	DD-MM-YYYY	DD-MM-YYYY	x.xx	xxxxxx
xxxxxx	DD-MM-YYYY	DD-MM-YYYY	x.xx	xxxxxx
xxxxxx	DD-MM-YYYY	DD-MM-YYYY	x.xx	xxxxxx
xxxxxx	DD-MM-YYYY	DD-MM-YYYY	x.xx	xxxxxx

Note: IMM-101 administrations since completion of IMM-101-001 were taken whilst patient was in Named Patient Programme and injection location was not recorded during this period.

Code: S:\Services\Immodulon\IMM-101-008\Analysis\Development\Code\Listing9.sas ddmmmyy:hh:mm:ss

Data: S:\Services\Immodulon\IMM-101-008\xxxxx.sas7bdat

Note to programmer: Please update data footnote with appropriate file directory.

Note to programmer: If date of administration is recorded as not known, present Unknown in place of date for the relevant dose.

Note to programmer: Date of last administration of IMM-101 in IMM-101-001 study should be displayed only once per patient.

S:\Services\Immodulon\IMM-101-008\SMF\SAP\IMM-101-008_SAPvFinal 1.1

Page 60 of 72

CONFIDENTIAL

Exploristics Limited

Identifier: EXP12002

Clinical Study Identifier: IMM-101-008

Final Analysis

Protocol: IMM-101-008

Analysis Population: Safety Population

Page x of y

Listing 10
On-Study IMM-101 Administration

Unique Patient ID	Visit Name/ Number	Visit Date	Date of Last Dose of IMM-101 (DD-MM-YYYY)	Have at Least 14 Days Passed Since Last Dose? (DD-MM-YYYY)	Time Elapsed Between This and Previous Dose (days)	Dose Administered (Y/N)	Dose (mg)	Dose Changed From Previous Dose	Reason for Dose Reduction or Delay (if applicable)	Injection Site
xxxxxx	xxxxxx	DD-MM-YYYY	DD-MM-YYYY	xxx	xx	xx	x.xx	x	xxxxxx	xxxxxx
xxxxxx	xxxxxx	DD-MM-YYYY	DD-MM-YYYY	xxx	xx	xx	x.xx	x	xxxxxx	xxxxxx
xxxxxx	xxxxxx	DD-MM-YYYY	DD-MM-YYYY	xxx	xx	xx	x.xx	x	xxxxxx	xxxxxx
xxxxxx	xxxxxx	DD-MM-YYYY	DD-MM-YYYY	xxx	xx	xx	x.xx	x	xxxxxx	xxxxxx
xxxxxx	xxxxxx	DD-MM-YYYY	DD-MM-YYYY	xxx	xx	xx	x.xx	x	xxxxxx	xxxxxx
xxxxxx	xxxxxx	DD-MM-YYYY	DD-MM-YYYY	xxx	xx	xx	x.xx	x	xxxxxx	xxxxxx
xxxxxx	xxxxxx	DD-MM-YYYY	DD-MM-YYYY	xxx	xx	xx	x.xx	x	xxxxxx	xxxxxx
xxxxxx	xxxxxx	DD-MM-YYYY	DD-MM-YYYY	xxx	xx	xx	x.xx	x	xxxxxx	xxxxxx

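### The SAP's time between doses is the date difference plus one, so every interval in Listing 10 prints one day too long

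*SAP*

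**What the plan says.** SAP section 8.3 (Derived and Transformed Data) gives the rule for on-study doses: "Time elapsed since previous dose (days) = (date of current dose - date of previous dose + 1"). The note under Listing 10 in SAP section 13.2 carries the same formula. The result fills a listing column for the days between the current and the previous dose. Section 8.3 also says that variables in days are printed as whole numbers.

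In the same listing, the column "Have at Least 14 Days Passed Since Last Dose" holds a separate answer, and the visit date and the date of the last dose are printed too.

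The protocol words its minimum gap as elapsed time. Section 5.2 (Treatment) says: "At no point should the elapsed period between IMM-101 doses be less than 14 days". The list of procedures for later visits in section 5.2.1.2 says: "Check that at least 14-days have elapsed since the last dose of IMM-101".

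The protocol also shows how it counts an interval. Of the Phase 1 study, section 3.3 says: "The placebo injection was administered on Day -3 and the IMM-101 injections over a 4-week period (Day 0, 14 and 28"). Section 7.3 describes the same doses: "The dosing schedule was 3 doses of IMM-101 given at two-week intervals i.e. a period of induction or priming".

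**The concern.** The days elapsed between two doses are the plain difference of the dates. The added day belongs in a duration that counts both end days, as the SAP's exposure formula does: "Overall study drug exposure (months) = (date of last dose - date of first dose in study IMM-101-008 + 1) / 30.4375". Applied to successive gaps, it counts each shared dose day twice.

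If the rule is programmed as written, every interval in the column is overstated. At the protocol's limit, a patient dosed 13 days after the previous injection would show 14 in the elapsed-days column, and a reader of that column alone would conclude that the minimum had been met. A correct answer in the 14-day column of the same row would be No, so the two columns would conflict. Long-term safety of extended dosing is the first study objective, and Listing 10 is the patient-level record of on-study dosing intervals.

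**Working it through.** **Inputs**

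- Rule: date of current dose − date of previous dose + 1 (SAP section 8.3 and the Listing 10 footnote).
- Minimum gap: 14 days elapsed (Protocol section 5.2).
- Nominal interval: 4 weeks = 28 days (Protocol section 7.4).
- Phase 1 dosing days: 0, 14 and 28, described as two weeks apart (Protocol sections 3.3 and 7.3).

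The documents state no numerical result for this variable, so there is no figure of the plan's own to reproduce.

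**Step 1. Which count does the protocol use?** Days 0, 14 and 28 give 14 − 0 = 14 and 28 − 14 = 14, that is, two weeks each. The plain difference reproduces the protocol's description. The SAP rule gives 14 − 0 + 1 = 15 and 28 − 14 + 1 = 15, which does not. These Phase 1 doses only illustrate the counting; they do not appear in Listing 10.

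**Step 2. Apply both counts to on-study gaps.**

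| True gap (days) | SAP rule prints | True gap at least 14? | Printed value at least 14? |
|---|---|---|---|
| 12 | 13 | No | No |
| 13 | 14 | No | **Yes** |
| 14 | 15 | Yes | Yes |
| 15 | 16 | Yes | Yes |
| 28 | 29 | Yes | Yes |
| 42 | 43 | Yes | Yes |

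The excess is always one day. Only a gap of exactly 13 days changes side at the limit.

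**Step 3. Is the rule consistent with the SAP's exposure formula?** For n successive gaps, the SAP rule sums to (last date − first date) + n. The exposure numerator is (last date − first date) + 1. The two agree only when n = 1. On the nominal schedule to Week 96 there are 96/4 = 24 gaps between 25 doses:

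- sum of the listing column: 24 × 29 = 696 days
- calendar span: 24 × 28 = 672 days
- exposure numerator: 672 + 1 = 673 days

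The SAP never sums this column. The comparison shows only that the added day, harmless once per span, does not work gap by gap.

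**Step 4. Where is the variable used?** Among the specified outputs it appears only in Listing 10. Table 7 counts full and reduced doses by visit. Tables 9a and 9b use time on study, first-to-last-dose exposure and number of doses. Table 8 uses survival from Day 0. None of them takes the dosing interval as an input.

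**Step 5. Check the correction.** With the plain difference, gaps of 13, 14 and 28 days print as 13, 14 and 28. Six successive 28-day gaps sum to 168 days, which is 24 weeks; under the present rule they sum to 174.

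**The case against.** The strongest defence is that this is a disclosed convention. Section 8.3 adds one day to age, to the time since diagnosis and since each surgical event, to time on study, to both exposure formulas and to overall survival. Several of these are also point-to-point times, and the Listing 10 footnote tells the reader what was done. That explains how the extra day got there, but it does not make the interval right. In variables reported in years or months to one decimal, the extra day is 1/365.25 ≈ 0.003 year or 1/30.4375 ≈ 0.03 month, once per patient. Here it is a whole day, in every row, on a scale printed in whole days beside a whole-day limit.

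The second defence is that compliance with the minimum gap does not rest on this column. The site checks the interval before each dose, the listing prints the dates and a separate answer, and SAP section 11 says: "Protocol deviations will be reported separately, based on the study protocol deviations log maintained by Immodulon". The SAP builds no flag or count on the derived value. This stands, and it is why the point is small.

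It is also fair to say that the protocol never writes down a day-counting rule. Its usage is still clear enough: the Phase 1 days and the word elapsed both point to the plain difference.

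**Conclusion.** The derivation is wrong as written. Each on-study dosing interval in Listing 10 is overstated by exactly one day, and a true gap of 13 days would print as meeting the protocol's 14-day minimum. No summary table, exposure figure or survival result changes. The severity is minor and the confidence high.

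This rests on two things. The first is that the protocol's elapsed period means the plain date difference, as its account of Phase 1 dosing implies. The second is that the program follows the SAP text; the code is not in the documents. The documents do not show whether any 13-day gap occurred, so the threshold effect is a possibility, while the one-day excess applies to every interval.

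**What to change.** In SAP section 8.3, define the time elapsed since the previous dose, in days, as the date of the current dose minus the date of the previous dose, with nothing added. Make the same change in the Listing 10 footnote and bring the listing program into line. Leave the exposure formulas alone: counting both end days is appropriate there. A flag in Listing 10 for values below 14 would be useful but is optional.

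The cost is two edits to the text and, assuming the code mirrors the SAP, a small change to one program and a rerun of that listing. No other specified output needs to be rerun. The change affects a derivation only and leaves the protocol's dosing rules as they are.
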